7.3 Potential Drug Interactions

7.3.1 Potential Drug Interactions with Cabozantinib

Cytochrome P450: Data from a clinical drug interaction study (Study XL184-008) show that clinically relevant steady-state concentrations of cabozantinib appear to have no marked effect on the area under the plasma concentration-vs-time curve (AUC) of co-administered rosiglitazone, a CYP2C8 substrate. Therefore, cabozantinib is not anticipated to markedly inhibit CYP2C8 in the clinic, and by inference, is not anticipated to markedly inhibit other CYP450 isozymes that have lower [I]/K_i values compared to CYP2C8 (ie, CYP2C9, CYP2C19, CYP2D6, CYP1A2, and CYP3A4). In vitro data indicate that cabozantinib is unlikely to induce cytochrome P450 enzymes, except for possible induction of CYP1A1 at high cabozantinib concentrations (30 μM).

Cabozantinib is a CYP3A4 substrate and a weak substrate for CYP2C9 (but not a CYP2D6, CYP2C8, CYP2C19, CYP2B6, or CYP1A2 substrate), based on data from in vitro studies. Results from a clinical pharmacology study, XL184-006, showed that concurrent administration of cabozantinib with the strong CYP3A4 inducer, rifampin, resulted in an approximately 77% reduction in cabozantinib exposure (AUC values) after a single dose of cabozantinib in healthy volunteers. Chronic co-administration of cabozantinib with strong inducers of the CYP3A4 family (eg, phenytoin, carbamazepine, rifampin, rifabutin, rifapentine, phenobarbital, and St. John's Wort) may significantly decrease cabozantinib concentrations. The chronic use of strong CYP3A4 inducers should be avoided. Other drugs that induce CYP3A4 should be used with caution because these drugs have the potential to decrease exposure (AUC) to cabozantinib. Selection of alternate concomitant medications with no or minimal CYP3A4 enzyme induction potential is recommended.

Results from a clinical pharmacology study, XL184-007, showed that concurrent administration of cabozantinib with the strong CYP3A4 inhibitor, ketoconazole, resulted in a 38% increase in the cabozantinib exposure (AUC values) after a single dose of cabozantinib in healthy volunteers. Co-administration of cabozantinib with strong inhibitors of the CYP3A4 family (eg, boceprevir, conivaptan, posaconazole, ketoconazole, itraconazole, clarithromycin, atazanavir, indinavir, nefazodone, nelfinavir, saquinavir, ritonavir, lopinavir, telaprevir, telithromycin, and voriconazole) may increase cabozantinib concentrations. Grapefruit, star fruit and Seville oranges may also increase plasma concentrations of cabozantinib and should be avoided. Strong CYP3A4 inhibitors should be avoided and other drugs that inhibit CYP3A4 should be used with caution because these drugs have the potential to increase exposure (AUC) to cabozantinib. Selection of alternate concomitant medications with no or minimal CYP3A4 enzyme inhibition potential is recommended.

Please refer to the drug interaction tables at the following websites for lists of substrates, inducers, and inhibitors of selected CYP450 isozyme pathways:

[Http://medicine.iupui.edu/clinpharm/ddis/table.aspx](http://medicine.iupui.edu/clinpharm/ddis/table.aspx)

<http://www.fda.gov/Drugs/DevelopmentApprovalProcess/DevelopmentResources/DrugInteractionsLabeling/ucm080499.htm>).

Protein Binding: Cabozantinib is highly bound ($\geq 99.7\%$) to human plasma proteins. Therefore, highly protein bound drugs should be used with caution with cabozantinib because there is a potential displacement interaction that could increase free concentrations of cabozantinib and/or a co-administered highly protein-bound drug (and a corresponding increase in pharmacologic effect).

Other Interactions: Food may increase exposure levels of cabozantinib by 57%, fasting recommendations should be followed. In vitro data suggest that cabozantinib is unlikely to be a substrate for P-glycoprotein, but it does appear to have the potential to inhibit the P-glycoprotein transport activity. Therefore, cabozantinib may have the potential to increase plasma concentrations of co-administered substrates of P-glycoprotein. Additional details related to these overall conclusions can be found in the investigator brochure.

Administration of the proton pump inhibitor (PPI) esomeprazole resulted in no clinically-relevant effect on cabozantinib plasma PK in healthy volunteers. Therefore, concomitant use of gastric pH modifying agents (ie, PPIs, H₂ receptor antagonists, and antacids) is not contraindicated in subjects administered cabozantinib.

Additional details regarding potential drug interactions with cabozantinib can be found in the investigator brochure.

Cabozantinib was shown to be a substrate of drug transporter MRP2 in an in vitro assay. Administration of MRP2 inhibitors to subjects may result in increases in cabozantinib plasma concentrations.

7.4 Study Treatment Accountability

The investigator or designee will maintain accurate records of receipt of all study treatment including dates of receipt. In addition, accurate records will be kept regarding the date, lot number, and how much study treatment is dispensed and used by each subject in the study. Reasons for deviation from the expected dispensing regimen must also be recorded. At completion of the study, to satisfy regulatory requirements regarding drug accountability, all unused study treatment will be reconciled and destroyed according to applicable state, federal, and local regulations.

Compliance will be assessed by the investigator and/or study personnel at each patient visit and information provided by the patient and/or caregiver (collection of drug diary) will be captured in the Drug Accountability Form. This information must be captured in the source document at each patient visit. Dose changes and interruptions of study drug must be specifically documented in the patient source documents and eCRF.

8 SAFETY

8.1 Adverse Events and Laboratory Abnormalities

8.1.1 Adverse Events (AEs)

An AE is any untoward medical occurrence in a patient or clinical trial subject administered a medicinal product and which does not necessarily have a causal relationship with this treatment.

An adverse event can therefore be any unfavorable and unintended sign (e.g. an abnormal laboratory finding), symptom, or disease temporarily associated with the use of a medicinal product, whether or not considered related to the medicinal product. An adverse event can arise from any use of the drug (e.g. off-label use, use in combination with another drug) and with any route of administration, formulation, or dose, including an overdose. This definition also includes AEs associated with medication errors and uses of the investigational product outside what is in the protocol, including misuse and abuse. Pre-existing medical conditions that worsen during the study should be recorded as AEs. Abnormal laboratory values, ECG findings, or vital signs are to be recorded as AEs if they meet the criteria described in in Section 6.

All untoward events that occur after informed consent through 30 days after the decision to discontinue study treatment (or the date the subject is deemed to be a screen failure) are to be recorded by the investigational site. This requirement includes AEs from unscheduled as well as scheduled visits.

The investigator (or physician designee) is responsible for verifying and providing source documentation for all adverse events and assigning the attribution for all adverse events for subjects enrolled.

Attribution is the relationship between an adverse event or serious adverse event and the study treatment. Attribution will be assigned as follows:

- Definite – The AE *is clearly related* to the study treatment.
- Probable – The AE *is likely related* to the study treatment.
- Possible – The AE *may be related* to the study treatment.
- Unlikely – The AE *is doubtfully related* to the study treatment.
- Unrelated – The AE *is clearly NOT related* to the study treatment.

Adverse event terms recorded on the CRFs will be mapped to preferred terms using the Medical Dictionary for Regulatory Activities (MedDRA). Seriousness, severity grade, and relationship to study treatment will be assessed by the investigator. Severity grade will be defined by the current version of the National Cancer Institute (NCI)-Common Terminology Criteria for Adverse Events (CTCAE).

8.1.2 *Serious Adverse Events (SAEs)*

The SAE definition and reporting requirements are in accordance with the International Conference of Harmonisation (ICH) Guideline for Clinical Safety Data Management: Definitions and Standards for Expedited Reporting, Topic E2A.

An SAE is defined as any untoward medical occurrence that at any dose:

- Result in death;
- Is life-threatening (i.e., in the opinion of the investigator, the AE places the subject at risk of death; it does not include an event that, had it occurred in a more severe form, might have caused death);

- Requires inpatient hospitalization or results in prolongation of an existing hospitalization;
 - Note: While most hospitalizations necessitate reporting of an SAE, some hospitalizations do not require SAE reporting, as follows: elective or previously scheduled surgeries or procedures for pre-existing conditions that have not worsened after initiation of treatment (e.g., a previously scheduled ventral hernia repair); pre-specified study hospitalizations for observation; or events that result in hospital stays of fewer than 24 hours and that do not require admission (e.g., an ER visit for hematuria that results in a diagnosis of cystitis and discharge home on oral antibiotics). SAEs must, however, be reported for any surgical complication resulting in prolongation of the hospitalization.
- Results in persistent or significant disability or incapacity:
 - Note: The term “disability” refers to events that result in a substantial disruption of a subject’s ability to conduct normal life function.
- Is a congenital anomaly or birth defect;
- Is an important medical event (IME):
 - Note: The term “important medical event” refers to an event that, based upon appropriate medical judgment, may not be immediately life-threatening or result in death or hospitalization, but may jeopardize the subject or require intervention to prevent one of the other serious outcomes listed. Examples of IMEs include intensive treatment in an emergency room or at home for allergic bronchospasm; blood dyscrasias, or convulsions that do not result in hospitalization; or development of product dependency or product abuse.

Reporting:

8.1.3 Relationship to Study Treatment

Assessment of the relationship of the AE to the study treatment by the investigator is based on the following two definitions:

- Not Related: A not-related AE is defined as an AE that is not associated with the study treatment and is attributable to another cause or there is no evidence to support a causal relationship;
- Related: A related AE is defined as an AE where a causal relationship between the event and the study treatment is a reasonable possibility. A reasonable causal relationship is meant to convey that there are facts (e.g., evidence such as dechallenge/rechallenge) or other clinical arguments to suggest a causal relationship between the AE and study treatment. Possibly and probably related AEs should be documented as related.

8.1.4 Serious Adverse Event Reporting:

As soon as an investigator becomes aware of an AE that meets the definition of ‘serious,’ this must be promptly documented on an SAE Report Form and in the electronic database (OnCore). All SAEs must be assessed by PI in order to determine reporting criteria to regulatory authorities

and include the following: (i) all SAEs that occur after starting cabozantinib and through 30 days after the decision to discontinue study treatment and (ii) any SAEs assessed as related to study treatment or study procedures, from the time of informed consent, even if the SAE occurs more than 30 days after the decision to discontinue study treatment.

All SAEs that are assessed by the PI as **related** to drug or study procedure and all pregnancy/lactation reports regardless of outcome must be sent to Exelixis within one (1) business day of the PI's knowledge of the event. The reports must be sent to [contact] or [contact].

- The PI will perform adequate due diligence with regard to obtaining follow-up information on incomplete reports. All follow-up information must be sent to Exelixis within one (1) business day of the PI's receipt of the new information. Upon Exelixis request, the PI will query for follow-up information.

8.1.5 Regulatory Reporting

The Investigator will assess the expectedness of each related SAE. The current cabozantinib Reference Safety Information (Appendix K of the most recent approved Investigator Brochure) will be used as the reference document for assessing the expectedness of the event with regard to cabozantinib. All serious unexpected adverse drug reactions (unexpected related SAEs) must be reported to all appropriate regulatory authorities and Ethics Committees by the investigator as required by 21 CFR 312.32 or by Directive 2011/20/EC:

- These reports are to be filed utilizing the Form FDA 3500A (MedWatch Form) or a CIOMS-1 form;
- Exelixis reserves the right to upgrade the Investigator assessment of an SAE based on Exelixis assessment.
- Institutions and PIs shall promptly provide all information requested by Exelixis regarding all adverse events occurring during the conduct of the study.
- The PI is responsible for complying with all regulatory authority reporting requirements for the study that are applicable to the study-supporter of a clinical trial. The PI shall provide a copy of all responses to regulatory agency requests, periodic reports, and final study reports to Exelixis within one (1) business day of the submission.
- Exelixis will provide relevant product safety updates and notifications, as necessary. In the case of multi-center studies, it is the responsibility of the sponsor to disseminate these updates to participating PIs.

8.2 Other Safety Considerations

8.2.1 Laboratory Data

All laboratory data required by this protocol and any other clinical investigations should be reviewed. Any abnormal value that leads to a change in subject management (e.g., dose reduction or delay or requirement for additional medication or monitoring) or that is considered

to be of clinical significance by the investigator should be reported as an AE or SAE as appropriate.

8.2.2 *Pregnancy/Lactation Exposure*

If a subject becomes pregnant during the study, she will be taken off study treatment and will be followed through the end of her pregnancy. Pregnancy (in subject or partner) or lactation exposure, although not an SAE, should be reported to Exelixis. Forms will be provided to the study sites upon request. The outcome of a pregnancy (for a subject or for the partner of a subject) and the medical condition of any resultant offspring must be reported to Exelixis. Any birth defect or congenital anomaly must be reported as an SAE, and any other untoward events occurring during the pregnancy must be reported as AEs or SAEs, as appropriate.

8.2.3 *Medication Errors/Overdose*

Any overdose, or study drug administration error that results in an AE, even if it does not meet the definition of serious, requires reporting within one (1) business day to Exelixis.

8.2.4 *Follow-Up of Adverse Events*

Any related SAEs or any AEs assessed as related that led to treatment discontinuation, including clinically significant abnormal laboratory values that meet these criteria, ongoing 30 days after the decision to discontinue study treatment must be followed until either resolution of the event or determination by the investigator that the event has become stable or irreversible. This follow-up guidance also applies to related SAEs that occur more than 30 days after the decision to discontinue study treatment. The status of all other continuing AEs will be documented as of 30 days after the decision to discontinue study treatment.

9 STATISTICAL CONSIDERATIONS

The primary outcome is objective response rate (complete and partial responses) at week 12 after the administration of cabozantinib. The Simon's two-stage design will be adopted for a possible early termination for futility. We hypothesize that there is > 24% response rate at 12-week and a rate < 5% will be considered as futility. In the first stage, 11 patients will be accrued (this does not include screen failures), and if there is no responses among them, the study will be stopped for futility. Otherwise, additional 6 patients will be accrued for a total of 17 patients. The null hypothesis will be rejected if there are 3 or more responses in 17 patients. The design yields a type I error rate of 0.05 and power of 80% when the true response rate is 24%. The final response rate will be estimated with 95% confidence interval by binomial test.

The safety profile of the treatment will be documented and summarized by summary statistics as frequency and percentage for each AE. We will do safety assesment after the first 6 patients without pausing the enrollment.

For disease free survival (DFS), which was defined as the interval between time of surgery and the first tumor recurrence, or death. Patients will be censored at time of last follow-up. For overall survival, death from any cause will be defined as the event. Patients will be censored at time of last follow-up. Overall survival (OS) and disease free survival (PFS) will be estimated

with the Kaplan-Meier method. The DFS and OS of each patient group at specific time points, such as 6 months, 1 year, and 3 year, etc. will be also estimated along with 95% CI.

For the biomarker study, descriptive statistics will be first used to summarize biomarker endpoints, including analyses of tumor biopsies. Biomarker data will also be displayed graphically, where appropriate. Depending on whether data is normally distributed, t-test or Wilcoxon rank sum test will be used to compare each biomarker between any two groups stratified by response or other factors, respectively. Logistics regression model will be further employed to test the adjusted effect of biomarker on the response rate after adjusting for other factors.

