Potential advantages of neoadjuvant therapy include downsizing and/or downstaging of tumors to change surgical approach from radical to partial nephrectomy or from open to minimally invasive surgery, and to allow for resection of unresectable tumors and potentially sparing organs. Lane et. reported presurgical sunitinib in 72 patients with renal cell carcinoma (11). Median tumor size improved from 7.2 cm to 5.3 cm after sunitinib treatment. Downsizing occurred in 65 tumors (83%), with 15 partial responses (19%) (11). 41% of patients with nephrometry score >9 could undergo partial nephrectomy, and eGFR change was -16% in partial nephrectomy group vs -24% in radical nephrectomy group (11). Rini et al. reported a phase II study of pazopanib in patients with localized renal cell carcinoma (12). 6 out of 13 patients for whom partial nephrectomy not possible at baseline underwent successful partial nephrectomy (12). Karam et al reported neoadjuvant axitinib in biopsy proven locally advanced clear cell renal cell carcinoma patients. In this cohort, all patients were T3a, and received up to 12 weeks of axitinib without any grade 3-4 adverse events. 11/24 patients achieved partial response, 13/24 patients achieved stable disease, and no disease progression were observed. The increased response rates for cabozantinib in mRCC above, along with the neoadjuvant axitinib data where 45% of neoadjuvantly treated patients achieved partial response, strongly support an expanded role for cabozantinib in the neoadjuvant setting.

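### Does the planned 95% confidence interval contradict the success rule when exactly 3 of 17 patients respond?

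*Combined protocol and SAP*

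**What the plan says.** Section 9 (Statistical Considerations) states the hypotheses in one direction: "We hypothesize that there is > 24% response rate at 12-week and a rate < 5% will be considered as futility". The design has two stages. The first enrols 11 patients, and "if there is no responses among them, the study will be stopped for futility". If the trial continues, "Otherwise, additional 6 patients will be accrued for a total of 17 patients". The decision is made on a count: "The null hypothesis will be rejected if there are 3 or more responses in 17 patients". The operating characteristics are given as "The design yields a type I error rate of 0.05 and power of 80% when the true response rate is 24" per cent.

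Estimation gets its own sentence at the end of that paragraph: "The final response rate will be estimated with 95% confidence interval by binomial test".

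Section 9 does not say whether alpha is one-sided, though a rule that rejects only for high counts is one-sided by construction. It does not name the interval method beyond the reference to a binomial test, does not mention the futility stage in connection with the interval, and does not say how to read the interval if it seems to disagree with the count.

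**The concern.** Readers of a small single-arm trial usually compare the reported interval with the null rate. Here the rule works at an upper-tail level of about 0.05, while a two-sided 95% interval leaves 2.5% in each tail. The interval is therefore the stricter of the two and can contain 5% when the rule has rejected 5%.

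This happens at 3/17, the smallest result that counts as success. At the design rate of 24% it makes up about a quarter of all successes. If it occurred, the report would declare 5% rejected and print a lower limit of 3.80% next to that claim. Someone could then question the success claim, or the choice of interval method could look as if it had been made after seeing the data. The interval also ignores the futility stage, which raises the question of whether its coverage is right.

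**Working it through.** **Inputs, all from Section 9.** Null rate 5%, alternative 24%, first stage 11 patients with a stop at 0 responses, total 17, rejection at 3 or more. Assumption: the 95% interval is two-sided and exact (Clopper-Pearson), the natural reading of an interval based on a binomial test.

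**Step 1: reproduce the design.** A final total of t responses is reached only if at least one of them falls among the first 11 patients. The number of arrangements is C(17,t) − C(6,t):
- t = 1: 17 − 6 = 11
- t = 2: 136 − 15 = 121
- t = 3: 680 − 20 = 660

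With true rate p,

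P(reject) = 1 − (1−p)^11 − 11p(1−p)^16 − 121p²(1−p)^15.

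- p = 0.05: 1 − 0.5688 − 0.2421 − 0.1401 = 0.0490
- p = 0.24: 1 − 0.0489 − 0.0327 − 0.1136 = 0.8048

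Both agree with the plan's 0.05 and 80%.

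**Step 2: the exact interval at each possible result near the boundary.** For x responses in n, the lower limit solves P(X ≥ x) = 0.025 and the upper limit solves P(X ≤ x) = 0.025.

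| Result | Rule rejects 5%? | Exact 95% interval | Excludes 5%? |
|---|---|---|---|
| 0/11 (stopped) | no | 0% to 28.49% | no |
| 1/17 | no | 0.15% to 28.69% | no |
| 2/17 | no | 1.46% to 36.44% | no |
| 3/17 | **yes** | 3.80% to 43.43% | **no** |
| 4/17 | yes | 6.81% to 49.90% | yes |

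Above 4/17 the lower limit only rises, so rule and interval disagree at 3/17 alone.

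**Step 3: how often 3/17 occurs.** P(exactly 3, after continuing) = 660p³(1−p)^14.

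- p = 0.24: 660 × 0.013824 × 0.02145 = 0.196, which is 0.1957 / 0.8048 = 24.3% of successes
- p = 0.30 (assumed, for range): 0.121
- p = 0.45 (the neoadjuvant axitinib rate cited in Section 1): 0.014

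**Step 4: is the level or the futility stage responsible?** Inverting the two-stage rejection probability instead of the single-stage one moves the 95% lower limit at 3/17 from 3.80% to 3.84%. It still contains 5%, so the futility stage explains almost nothing. The cause is the level.

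**Step 5: is the ordinary exact interval valid after a two-stage design?** Coverage was computed by summing the probabilities of all results whose interval contains the true rate, with n = 11 after an early stop and n = 17 otherwise, over true rates from 0.05% to 80%. The minimum is 95.1%, at a true rate near 49.9%. The interval keeps its nominal level.

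**Step 6: would another interval help?** An ordinary exact 90% interval at 3/17 is 4.99% to 39.56%, so it still just contains 5%; its coverage falls to 89.0% in a narrow band of true rates around 25% to 26%. A 90% interval built on stage-wise ordering is 5.04% to 39.64% and does agree with the rule. The gain between the two is 5.04 − 4.99 = 0.05 percentage points in a lower limit, and to one decimal both lower limits print as 5.0%.

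**The case for a change.** The strongest case for a change is that the conflict falls on the minimum success, which is not remote at the plan's own alternative, and that a sentence or two would settle it in advance. Stating before results that the count decides would avoid an argument that could look post hoc after 3/17. The interval method is also not named outright, and it matters there: at 3/17 the Clopper-Pearson and Wald 95% intervals contain 5%, while the Wilson (lower limit 6.2%), Jeffreys (5.2%) and Agresti-Coull (5.4%) intervals exclude it.

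Part of this stands. The mismatch is real on the exact reading, and a clarifying sentence would do no harm. But it would only put a label on what Section 9 already arranges: the rejection sentence refers to the count and to nothing else, and the interval sentence speaks of estimating the rate. The reference to a binomial test points to the exact interval, and an analyst following it would have little reason to pick Wilson or Jeffreys. Because no decision depends on the interval, choosing another method later could not turn failure into success. The fuller remedy, a second interval at another level by another method, would put 5.04% to 39.64% beside 3.80% to 43.43% in a 17-patient report and could confuse more readers than it helps.

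**Conclusion.** No change is needed. The plan pairs a one-sided phase II decision rule with a two-sided 95% estimation interval. These are two levels serving two purposes, and they are not required to agree at the boundary. They disagree at one outcome, 3/17, with probability 19.6% at a true rate of 24%, 12.1% at an assumed 30% and 1.4% at 45%.

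The design figures reproduce (type I error 0.0490, power 80.5%), the exact 95% interval has coverage of at least 95.1% under the two-stage design, and the count remains the sole success criterion. Should 3/17 occur, the report can say that the null was rejected by the prespecified rule and give the exact interval as a measure of precision.

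This conclusion assumes the two-sided exact reading of the interval. If one of the methods that exclude 5% at 3/17 were used instead, the apparent conflict would vanish and the decision would be the same.
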